Appendix 7 Labels of Apatinib Mesylate Tablets as a Second-Line Treatment for Advanced HCC.....	117
Appendix 8 Percent Bone Marrow Content in Human Skeleton	119
Appendix 9 Quality of Life Score (EORTC QLQ-C30 V3.0 及 HCC and HCC-18).....	120
Appendix 10 Flow Chart of Randomization and Enrollment for the Clinical Trial of Apatinib Mesylate Tablets as a Second-Line Treatment for Advanced Hepatic Carcinoma	125
REFERENCES.....	126

LIST OF TABLES

Table 1. Effects of apatinib on KTRs.....	56
Table 2. Efficacy of apatinib in the treatment of different solid tumors	61
Table 3. Changes in plasma VEGF at different time points in 10 subjects.....	62
Table 4. Inter-group comparison of efficacy results (FAS).....	65
Table 5. Comparison of the incidences of AEs and ADRs between the two groups (SS)	65
Table 6. Common AEs (incidence $\geq 10\%$) in both groups.....	66
Table 7. Results of sample size estimation	74
Table 8. Doses and dose level modification of each group.....	79
Table 11. Suggested treatments for proteinuria.....	85
Table 12. Criteria for the causality between AEs and investigational drug	93
Table 13. Contact information of each institution	94

PROTOCOL SYNOPSIS

Study Title	A Multicenter, Double-Blind, Randomized, Parallel-Controlled Phase III Clinical Study Evaluating Apatinib Mesylate Tablet as Second-Line Treatment in Patients with Advanced Hepatocellular Carcinoma (HCC)
Protocol No.	APTN-III-HCC
Sponsors	Jiangsu Hengrui Pharmaceuticals Co., Ltd. Shanghai Hengrui Pharmaceutical Co., Ltd.
Nature	Phase III clinical trial for IND application
Study Population	Patients with advanced HCC refractory to systemic treatment
Study Objective	To observe and evaluate the efficacy and safety of apatinib mesylate tablet as second-line treatment in patients with advanced HCC
Primary endpoint	Overall survival (OS)

Efficacy endpoints:

Progression free survival (PFS);
3-, 6-, and 12-month PFS rates;
Time to progression (TTP);
Objective response rate (ORR);
Disease control rate (DCR);

Study Endpoints	Secondary endpoints	The percentage of evaluable patients with stable disease (SD) of ≥ 4 weeks (confirmed SD); 6- and 12-month mortalities; Quality of life score;
-----------------	---------------------	---

Safety endpoints:

Vital signs, laboratory measurements, adverse events (AEs), serious adverse events (SAEs), treatment-related AEs and SAEs, and AEs of special interest (e.g., hypertension, proteinuria, and hand-and-foot syndrome [palmar-plantar erythrodysesthesia syndrome]);

Judged as per NCI-CTCAE V4.0 criteria

Study Design	A randomized, double-blind, placebo-controlled, multi-center phase III clinical trial; Subjects will be stratified and randomized based on the ECOG PS (0 or 1), the past medication of sorafenib, and the presence of vascular invasion and/or extrahepatic metastasis
--------------	--

Planned Enrollment	A total of 360 subjects are planned to be enrolled, including 240 subjects in the apatinib group and 120 subjects in the placebo group. According to the resolution of scientific committee, additional subjects will be enrolled, i.e., 390 subjects in total.
--------------------	---

Clinical Diagnostic Criteria:

"Guideline on Diagnosis and Treatment for Primary Liver Cancer" (2011 Edition) states:

The clinical diagnosis of HCC can be confirmed when the following conditions (1) + (2)a or conditions (1) + (2)b + (3) are met:

(1) With evidence of cirrhosis and HBV and/or HCV infection (positive HBV and/or HCV antigen);

(2) Typical imaging features of HCC: Multidetector CT scan and/or dynamic contrast-enhanced MRI showing hepatic space-occupying lesions with arterial hypervascularity and venous or delayed phase washout;

- One of the two imaging examinations (CT and MRI) showing the above features of liver cancer for those with lesions ≥ 2 cm in diameter;
- Both CT and MRI imaging examinations showing the above features of liver cancer for those with lesions of 1-2 cm in diameter, so as to enhance the specificity of the diagnosis;

(3) Serum AFP ≥ 400 $\mu\text{g/L}$ for 1 month or ≥ 200 $\mu\text{g/L}$ for 2 months, and when the increase in AFP level due to other reasons can be excluded, including pregnancy, germline embryogenic tumor, active liver disease and secondary liver cancer.

Inclusion Criteria:

1. Age: ≥ 18 years old;
2. Patients strictly meeting the clinical diagnostic criteria in "Guideline on Diagnosis and Treatment for Primary Liver Cancer" (2011 Edition) or with histologically or cytologically confirmed recurrent/metastatic HCC, unsuitable for palliative surgery or radiation therapy, with at least one measurable lesion (must be ≥ 10 mm in longest diameter by spiral CT or ≥ 15 mm in shortest diameter for enlarged lymph nodes, as per RECIST 1.1, as shown in Annex 1);
3. Patients with HCC refractory or intolerant to systematic chemotherapy (with oxaliplatin, alone or in a therapeutic combination) and/or molecular targeted therapy with sorafenib;

Note: Definition of treatment failure: disease progression during treatment or relapse after treatment is completed (must have received ≥ 1 cycle of systemic chemotherapy with oxaliplatin (or plus other drugs) or ≥ 14 days of molecular targeted therapy with sorafenib);

Definition of intolerance: Grade \geq IV hematological toxicity or Grade \geq III non-hematological toxicity or Grade \geq II major organ injury such as the heart, liver, or kidneys during treatment.

4. The interval between the last systemic treatment failure (with treatment discontinued) and the enrollment (time of signing the informed consent form) was ≥ 2 weeks, and the adverse event(s) had basically returned to normal (NCI-CTCAE \leq Grade I);
5. Child-Pugh score: Class A or Class B (≤ 7); the Child-Pugh scoring system is shown in Appendix 2;
6. BCLC staging: B-C ("Barcelona Clinic Liver Cancer (BCLC) Staging System, 2010" is shown in Appendix 3);
7. ECOG PS of 0-1 within 1 week before enrollment, as shown in Appendix 4;
8. Expected survival ≥ 12 weeks;
9. HBV DNA < 2000 IU/mL (10^4 copies/mL);
10. Major organs must function normally, meeting the following criteria:
 - (1) Hematology: (without blood transfusion, G-CSF, or medication within 14 days prior to screening)
 - a. HB ≥ 90 g/L;
 - b. ANC $\geq 1.5 \times 10^9/\text{L}$;
 - c. PLT $\geq 80 \times 10^9/\text{L}$;
 - (2) Biochemistry: (no ALB transfusion within 14 days)
 - a. ALB ≥ 29 g/L;

- b. ALT and AST $< 5 \times$ ULN;
- c. TBIL $\leq 1.5 \times$ ULN;
- d. Creatinine $\leq 1.5 \times$ ULN;

(Only one of the two items, albumin or bilirubin, has a Child-Pugh score of 2)

- 11. Women of childbearing potential must have a negative pregnancy test (serum or urine) within 7 days prior to enrollment, and be willing to take appropriate contraceptive measures during the trial and within 8 weeks after the last dose of the investigational drug. Male subjects should either undergo surgical sterilization, or agree to take appropriate contraceptive measures during the trial and within 8 weeks after the last dose of the investigational drug;
- 12. Subjects must participate voluntarily, sign the informed consent form, have good compliance and corporate with follow-up visits.

Exclusion Criteria:

- 1. Patients who have received any local treatment within 4 weeks prior to participating in this study (including but not limited to surgery, radiation, hepatic artery embolization, TACE, hepatic arterial infusion, radiofrequency ablation, cryoablation, or percutaneous ethanol injection);
- 2. Patients with known intrahepatic cholangiocarcinoma, mixed hepatocellular carcinoma and fibrolamellar hepatocellular carcinoma; other uncured malignancies currently or within the past 5 years, except for cured skin basal cell carcinoma or cervical carcinoma in situ;
- 3. Patients planning to receive liver transplant (except for patients who have undergone liver transplant);
- 4. Patients with symptomatic ascites requiring therapeutic paracentesis or drainage, or with a Child-Pugh score > 2 ;
- 5. Patients with hypertension which cannot be controlled to the normal range by antihypertensives (systolic pressure > 140 mmHg, diastolic pressure > 90 mmHg);
- 6. Patients with Grade II or greater myocardial ischemia or myocardial infarction, uncontrolled arrhythmias (QTc interval ≥ 450 ms in males and ≥ 470 ms in females);
- 7. Patients with NYHA (see Appendix 5) Class III-IV cardiac insufficiency or LVEF (left ventricular ejection fraction) $< 50\%$ by echocardiography;
- 8. Presence of multiple factors affecting oral medications (such as inability to swallow, chronic diarrhea, and intestinal obstruction, which significantly affect drug administration and absorption);
- 9. Patients with a history of gastrointestinal bleeding within the past 6 months or a high risk of bleeding such as esophageal varices with bleeding risk, active ulcers, and fecal occult blood $\geq (++)$; in the case of fecal occult blood $(+)$, a gastroscopy is required;
- 10. Abdominal fistula, gastrointestinal perforation or abdominal abscess within 28 days prior to the study;
- 11. Abnormal coagulation function (INR > 1.5 or prothrombin time (PT) $> \text{ULN} + 4$ s), bleeding tendency or receiving thrombolytics or anticoagulant therapy;
- 12. Patients with central nervous system metastases or known brain metastases;
- 13. Patients with previous or current objective evidence of pulmonary fibrosis, interstitial pneumonia, pneumoconiosis, radiation pneumonitis, drug-induced pneumonitis, and severe lung function impairment;
- 14. Urine protein $\geq ++$ or 24-h urine protein > 1.0 g as indicated by urinalysis;

15. Had received treatment with a potent CYP3A4 inhibitor within 7 days prior to study participation, or had received treatment with a potent CYP3A4 inducer within 12 days prior to study participation;
16. Pregnant or lactating women; patients of child-bearing potential unwilling or unable to take effective contraceptive measures;
17. Patients with a known history of mental illness or psychotropic substance abuse;
18. Patients with bone metastasis who had received a palliative radiotherapy in an area of > 5% of bone marrow area within 4 weeks prior to the participation in this study.

Termination Criteria:

1. Subject withdraws informed consent and requests to withdraw from the study;
2. Medical imaging examinations show disease progression;
3. Subjects showing unacceptable toxicity after dose modification;
4. Other reasons for which the investigator considers a withdrawal necessary;
5. Study termination by the sponsor for the sake of safety.

**Investigational Drugs and
Method of Administration**

Treatment group: Apatinib is given via oral administration after meals (the dosing time on each day should remain the same whenever possible) at an initial dose of 750 mg/day, once a day, 3 tablets per dose, in 28-day cycles. The dose can be adjusted based on the toxic reactions of the subjects as per protocol (first dose reduction: 500 mg/day, q.d.; second dose reduction: 250 mg/day, q.d.). If the toxic side effects are completely resolved after dose reduction, the dose can be resumed to the previous dose level; however, if the dose is reduced again, it should not be resumed again according to the protocol.

Placebo group: Placebo is given via oral administration after meals (the dosing time on each day should remain the same whenever possible) at an initial dose of 750 mg/day, once a day, 3 tablets per dose, in 28-day cycles. The dose can be adjusted based on the toxic reactions of the subjects as per protocol (first dose reduction: 500 mg/day, q.d.; second dose reduction: 250 mg/day, q.d.);

Study Period

November 2013-March 2018

In this trial, placebo is used as a control and a superiority test is performed between the two groups.

All statistical analyses will be performed using SAS. All statistical analyses are performed using two-tailed tests. $P \leq 0.05$ is considered statistically significant, and 95% confidence is used for confidence intervals.

Pre-set subgroup analysis: Subgroups will be pre-defined based on the following factors for a confirmatory subgroup analysis in this study: age ≤ 65 years or > 65 years; ECOG PS 0 or 1; with or without vascular invasion; with or without extrahepatic metastases; with or without vascular invasion and extrahepatic metastases; positive or negative HBV; and with or without past history of sorafenib treatment.

The baseline data is analyzed based on the full analysis set (FAS). All efficacy endpoints are analyzed based on the FAS and the per protocol set (PPS). The analysis of primary efficacy endpoint OS is carried out mainly in the FAS, but the PPS is used for the final analysis. The safety analysis is carried out based on the safety analysis set (SS).

The measurement data obtained from various treatment groups during various visits will be statistically described by mean \pm standard deviation or median (minimum, maximum). For comparison with baseline values of the screening period, paired t-tests are used to compare pre and post intra-group differences. Changes occurring in each group before and after treatment should be

Statistical Methods

compared by the analysis of variance (ANOVA) or rank sum test. The frequency data obtained from various treatment groups during various visits will be statistically described by frequency (proportions). Changes occurring in each group before and after treatment should be compared by χ^2 test (exact test) or nonparametric test.

- Dropout analysis: Descriptive analysis is mainly used. If necessary, the total dropout rate of each group and the comparison of dropout due to AEs will be tested by χ^2 test or Fisher's exact test.
- Balance analysis of baseline values: ANOVA or χ^2 test is used to compare demographic data and other baseline values to evaluate the balance of various groups.
- Efficacy analysis:

For the comparison of 3-, 6-, and 12-month PFS rates, objective response rate (ORR), disease control rate (DCR), the percentage of patients with stable disease (SD) of ≥ 4 weeks (confirmed SD in particular), and 6- and 12-month mortalities, CMH- χ^2 tests with and without central stratification are used to compare the efficacy between the two groups. In addition, the 95% confidence interval of the difference between the two groups is also calculated. Based on the product limit method and the actual condition of the data, 25%, 50% (median) and 75% of PFS and TTP, as well as PFS and OS at different time points after the start of treatment, are calculated and the endpoints are compared between the two groups using the Log-Rank test.

- Safety analysis: Descriptive statistical analysis will be mainly used. The AEs and SAEs, treatment-related AEs and SAEs, and AEs and SAEs of special interest (e.g., hypertension, proteinuria, and hand-and-foot syndrome) are listed and summarized. If necessary, the incidence and severity of AEs and SAEs between different groups are compared using Fisher's exact test.

Pre-Set Point for Efficacy Analysis	Date of the 312 th death ($\geq 80\%$ of the subjects have died) based on the full analysis set
Version No.	1.4

SCHEDULE OF ACTIVITIES

Treatment Cycle Visit Test Items	Screening Period	C1		C2		C3	C4	C5	C6	C7	C8	C9	C10	C11	Withdrawal	28 Days after Withdrawal		Follow-up 1	Follow-up 2
		V1 (-3W)	V2	V3	V4	V5	V6	V7	V8	V9	V10	V11	V12	V13	V14	Vn	Vn+1	V100	V101
Date of Visit		√	√	√	√	√	√	√	√	√	√	√	√	√	√	√		√	√
Demographics		√																	
Tumor History		√																	
Surgical History of Primary Lesions		√																	
History of Local Ablation		√																	
History of Intervention		√																	
History of Radiotherapy		√																	
History of Systemic Treatment		√																	
Past Medical History		√																	
History of Drug Allergy		√																	
Chest X-Ray ^a		√																	
Hepatitis B/Hepatitis C Markers and HBV-DNA		√																	
Serum AFP ^b		√				√			√										
Vital Signs		√		√		√	√	√	√	√	√	√	√	√	√	√	√	√	
Physical Examination		√		√		√	√	√	√	√	√	√	√	√	√	√	√	√	
ECOG Performance Status Score		√		√		√	√	√	√	√	√	√	√	√	√	√	√	√	
Hematology		√		√		√	√	√	√	√	√	√	√	√	√	√		√	
Blood Biochemistry		√		√		√	√	√	√	√	√	√	√	√	√	√		√	
Urinalysis ^c		√		√		√	√	√	√	√	√	√	√	√	√	√			

Test Items	Treatment Cycle Visit	Screening Period	C1		C2		C3	C4	C5	C6	C7	C8	C9	C10	C11	Withdrawal	28 Days after Withdrawal		Follow-up 1	Follow-up 2
			V1 (-3W)	V2	V3	V4	V5	V6	V7	V8	V9	V10	V11	V12	V13	V14	Vn	Vn+1		
Coagulation Function		✓			✓		✓	✓	✓	✓	✓	✓	✓	✓	✓					
Pregnancy Test ^d		✓																		
Stool Routine ^e		✓																		
Echocardiography ^f		✓																		
ECG ^g		✓		✓		✓	✓		✓		✓		✓		✓	✓				
Quality of Life Score ^h		✓				✓	✓		✓		✓		✓		✓	✓	✓			
Child-Pugh Score		✓																		
Imaging Evaluation-Target Lesion ⁱ		✓				✓	✓		✓		✓		✓		✓	✓			✓	
Imaging Evaluation-Non-target Lesion ⁱ		✓				✓	✓		✓		✓		✓		✓	✓			✓	
Imaging Evaluation-New Lesion ⁱ						✓	✓		✓		✓		✓		✓	✓			✓	
Inclusion and Exclusion Criteria		✓																		
Enrollment Assessment		✓																		
Drug Return and Dispensing			✓		✓	✓	✓	✓	✓	✓	✓	✓	✓	✓	✓	✓				
Blood Pressure Record			✓		✓	✓	✓	✓	✓	✓	✓	✓	✓	✓	✓	✓				
Drug Interruption Form																		✓		
Dose Modification Form																		✓		
Additional Examinations																		✓		
Concomitant Medication																		✓		
Adverse Event																		✓		
Serious Adverse Event																		✓		

Treatment Cycle Visit Test Items	Screening Period	C1		C2		C3	C4	C5	C6	C7	C8	C9	C10	C11	Withdrawal	28 Days after Withdrawal		Follow-up 1	Follow-up 2	
		V1 (-3W)	V2	V3	V4	V5	V6	V7	V8	V9	V10	V11	V12	V13	V14	Vn	Vn+1	V100	V101	V201
Summary of Study																		√		
Survival Follow-Up																				√

Note: (1) The results of ECOG PS, hematology, urinalysis, blood biochemistry, coagulation function, quality of life score, and ECG must be collected within 1 week before randomization.

- (2) a: Chest X-ray: If the chest CT has been performed during the screening period, chest X-ray is not required.
- (3) b: Serum AFP: Only detected at the end of Cycle 2 and Cycle 5; not strictly required after Cycle 5.
- (4) c: Urinalysis: Not required for female subjects during their menstrual period.
- (5) d: Pregnancy test: Additional pregnancy tests can be carried out during the treatment period if necessary.
- (6) e: Stool routine (occult blood): In the case of fecal occult blood (+) during the screening period, a gastroscopy is required; and additional fecal occult blood tests can be carried out during the treatment period if necessary.
- (7) f: Echocardiography: Must be performed during the screening period. For clinically significant ECG abnormalities observed during the study period, an additional echocardiography examination is required.
- (8) g: ECG: The QTc interval must be indicated for 3 times, with about 5 min apart. ECG examination shall be carried out before drug administration during the screening period and then always after drug administration in each visit. For clinically significant ECG abnormalities, an additional echocardiography examination is required; if there are symptoms such as precordial pain and palpitations, the myocardial zymogram (creatinine kinase, lactate dehydrogenase) should be tested immediately. The examination should be carried out every two cycles after Cycle 3.
- (9) h: Quality of life score: Must be measured before the efficacy evaluation; and measured every two cycles after Cycle 3.
- (10) i: Imaging examination: Screening period: including CT or MRI of the chest and abdomen. Brain CT/MRI is required for clinically suspected metastases to the central nervous system. A bone scan is required for clinically suspected bone metastasis. Treatment period: The examination should be carried out in Cycles 2 and 3, and then every two cycles after Cycle 3.
- (11) i: Efficacy evaluation: The first efficacy evaluation is carried out at the end of Cycle 2; efficacy confirmation is carried out at 4 weeks after the first efficacy evaluation (i.e., at the end of Cycle 3). Afterwards, the efficacy evaluation is carried out every two cycles; For subjects who withdraw from the study due to unacceptable toxicity, the efficacy evaluation should be conducted upon withdrawal if the efficacy evaluation is not carried out within 4 weeks before withdrawal. Thereafter, the imaging examination is performed every 2 cycles until progressive disease.
- (12) Follow-up 1 (can be repeated for V101): The subjects who withdraw from the study due to unacceptable toxicity should be followed-up for tumor progression until the tumor progression is confirmed by imaging or the start of new anti-tumor treatment.
- (13) Follow-up 2 (can be repeated for V201): Survival follow-up, visit number from 201, 202, 203...

REGULATIONS FOR DOSE MODIFICATION

NCI Toxicity Grade	Regulations for Dose Modification	Regulations for Toxicity Recovery upon Re-Administration after Treatment Discontinuation	Regulations for Toxicity Recovery at the Beginning of Next Cycle
Grade I Hematological Toxicity	Maintain original dose		
Grade II Hematological Toxicity	Maintain original dose		
Grade III Hematological Toxicity	Interrupt treatment and give symptomatic treatment until toxicity returns to Grade \leq II, and then resume treatment at the original dose level	After treatment discontinuation during treatment cycle, hematological toxicity must recover to Grade \leq II before treatment can be resumed	At the beginning of the next cycle of administration, hematological toxicity must recover to Grade \leq II before treatment can be started
Grade IV Hematological Toxicity	Interrupt treatment and give symptomatic treatment until toxicity returns to Grade \leq II, and then resume treatment at the next lower dose level; upon complete recovery of toxicity, dose may be re-adjusted to the previous level to continue treatment; if a Grade IV hematological toxicity occurs again after such re-adjustment, dose should be reduced accordingly and no further adjustments shall be allowed		
Grade I Non-Hematological Toxicity	Maintain original dose		
Grade II Non-Hematological Toxicity	Give symptomatic treatment and continue study administration at the same time, if toxicity returns to Grade \leq I after one week, continue dosing; if the toxicity does not recover or even worsens, interrupt treatment until toxicity returns to Grade \leq I, and then resume treatment at the original dose level	After treatment discontinuation during treatment cycle, non-hematological toxicity must recover to Grade \leq I before treatment can be resumed	At the beginning of next cycle, non-hematological toxicity must recover to Grade \leq I before treatment can be started
Grade III Non-Hematological Toxicity	Interrupt treatment and give symptomatic treatment until toxicity returns to Grade \leq I, and then resume treatment at the original dose level, and reduce by 1 dose level for the next cycle; investigator may decide accordingly for certain patients based on the specific conditions without waiting for the next cycle; upon complete recovery of toxicity, dose may be re-adjusted to the previous level to continue treatment; if a Grade III non-hematological toxicity occurs again after such re-adjustment, dose should be reduced accordingly and no further adjustments shall be allowed		

NCI Toxicity Grade	Regulations for Dose Modification	Regulations for Toxicity Recovery upon Re-Administration after Treatment Discontinuation	Regulations for Toxicity Recovery at the Beginning of Next Cycle
Grade IV Non-Hematological Toxicity	Interrupt treatment and give symptomatic treatment until toxicity returns to Grade \leq I, and then resume treatment at the next lower dose level for at least 1 cycle; upon complete recovery of toxicity, dose may be re-adjusted to the previous level to continue treatment; if a Grade IV non-hematological toxicity occurs again after such re-adjustment, dose should be reduced accordingly and no further adjustments shall be allowed (if a life-threatening adverse reaction, such as Grade IV renal impairment, neurotoxicity, cardiotoxicity, or hepatotoxicity occurs, discontinue the treatment and withdraw)		

ABBREVIATIONS AND DEFINITIONS

The following abbreviations and special terms are used in this study protocol

Abbreviations and Special Terms	Definitions
ACEI	Angiotensin converting enzyme inhibitor
AE	Adverse event
AFP	Alpha-Fetoprotein
AKP	Alkaline phosphatase
ALT	Alanine aminotransferase
ANC	Absolute neutrophil count
APTT	Activated partial thromboplastin time
ARB	Angiotensin II receptor blocker
AST	Aspartate aminotransferase
BUN	Blood urea nitrogen
B-Scan	B-mode ultrasound
Ca	Calcium
Cl	Chlorine
Cr	Creatinine
CR	Complete response
CT	Computed tomography
DCR	Disease control rate
DLT	Dose-limiting toxicity
DRQ	Data ready queue
ECOG PS	Eastern Cooperative Oncology Group Performance Status
eCRF	Electronic case report form
EGFR	Epidermal growth factor receptor
Fbg	Fibrinogen
GCP	Good Clinical Practice
FAS	Full analysis set
Glu	Glucose
Hb	Hemoglobin
HCC	Hepatocellular carcinoma
HFS	Hand-foot-skin reaction
HMG-CoA	β -Hydroxy β -methylglutaryl-coenzyme A
ITT	Intention to treat
K	Potassium
LD50	Median lethal dose
MRI	Magnetic resonance imaging
MTD	Maximum tolerated dose
Na	Sodium
NCI-CTC	National Cancer Institute Common Toxicity Criteria
OB	Occult blood
ORR	Objective response rate
OS	Overall survival
PD	Progressive disease
PDGFR	Platelet derived growth factor receptor
PFS	Progression free survival

Abbreviations and Special Terms	Definitions
PI	Principal investigator
PLT	Platelet
PR	Partial response
PRO	Protein
PPS	Per-protocol set
PT	Prothrombin time
q.d.	Quaque die
QoL	Quality of life
RBC	Red blood cell
RC	Red color sign
RECIST	Response evaluation criteria in solid tumors
RR	Response rate
RTKs	Receptor tyrosine kinase
γ-GT	γ-glutamyltransferase
SAE	Serious adverse event
SAS	Safety analysis set
SD	Stable disease
TT	Thrombin time
TPP	Time to progression
ULN	Upper limit of normal
URIC	Uric acid
VEGF	Vascular endothelial growth factor
VEGFR	Vascular endothelial growth factor receptor
WBC	White blood cell

Apatinib mesylate tablet is a novel drug developed and filed by Jiangsu Hengrui Pharmaceuticals Co., Ltd. and Shanghai Hengrui Pharmaceutical Co., Ltd. The product (strength of 0.2 g) has been approved for phase I clinical trial by National Medical Products Administration (NMPA) in Apr. 2007 (approval no. 2007L00837), and for phase II/III clinical trials in May 2009 (approval no. 2009L03464). Having completed the technical review of the means of production at dosage strength of 0.25 g in Feb. 2014, the Center for Drug Evaluation (CDE) reissued clinical trial approval for strength of 0.25 g in Jun. 2014 (approval no. 2014L00877).

At present, the National Clinical Research Center in the 81st Hospital of the Chinese People's Liberation Army (Nanjing) is leading the nationwide multi-center phase III clinical trial of apatinib mesylate tablets as second-line treatment in patients with advanced hepatocellular carcinoma, in accordance with the "Provisions for Drug Registration" and "Good Clinical Practice" (GCP). To this end, this study protocol has been formulated.

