11. Abnormal coagulation function (INR > 1.5 or prothrombin time (PT) > ULN + 4 s), bleeding tendency or receiving thrombolytics or anticoagulant therapy;
12. Patients with central nervous system metastases or known brain metastases;

13. Patients with previous or current objective evidence of pulmonary fibrosis, interstitial pneumonia, pneumoconiosis, radiation pneumonitis, drug-induced pneumonitis, and severe lung function impairment;
14. Urine protein \geq ++ or 24 h urine protein > 1.0 g as indicated by urinalysis;
15. Had received treatment with a potent CYP3A4 inhibitor within 7 days prior to study participation, or had received treatment with a potent CYP3A4 inducer within 12 days prior to study participation;
16. Pregnant or lactating women; patients of child-bearing potential unwilling or unable to take effective contraceptive measures;
17. Patients with a known history of mental illness or psychotropic substance abuse;
18. Patients with bone metastasis who had received a palliative radiotherapy in an area of $> 5\%$ of bone marrow area within 4 weeks prior to the participation in this study.

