7.2.1 Criteria for dose interruption or dose reduction

The dose is only allowed to be interrupted and reduced in the case of Grade \geq III hematological toxicity or Grade \geq II non-hematological toxicity. Among the events of non-hematological toxicity, controllable nausea and vomiting as well as fever (under 38°C) with a clear cause can be handled with active symptomatic treatments without the need for dose interruption and dose reduction.

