8.3 Recommended Symptomatic Treatment for Common Adverse Drug Reactions

8.3.1 Hand-foot-skin reaction

Hand-foot-skin reaction (HFSR) is a skin toxicity with palmar-plantar dysesthesia or acral erythema and manifests especially in areas under pressure or force. It may occur in patients with tumor during chemotherapy or molecular targeted therapy. HFSR is characterized by numbness, dysesthesia, paraesthesia, tingling, no pain or pain, skin swelling, or erythema, desquamation, chapping, scleroma-like blisters, and severe pain.

Grading of HFSR:

Grade 1: numbness/dysesthesia/paraesthesia, painless swelling or erythema of the hands and/or feet and/or discomforts that does not affect normal activities.

Grade 2: painful erythema and swelling of the hands and/or feet and/or discomforts affecting patients' activities of daily living.

Grade 3: wet desquamation, ulcers, blisters or severe pain of hands and/or feet and/or severe discomfort that causes the patients to be unable to work or perform activities of daily living. Intense pain and loss of skin function, relatively rare.

Symptomatic treatment and management of HFSR:

Some necessary symptomatic and supportive treatments must be taken, including: strengthen skin care, keep skin clean, and avoid secondary infections; avoid pressure or friction; use moisturizers or lubricants, topically use lotions or lubricants containing urea and corticosteroids; topically use antifungal or antibiotic treatment if necessary.

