8.3.5 Interstitial pulmonary fibrosis

The clinical physicians should fully understand the conditions of subjects and be familiar with the drugs that may lead to pulmonary toxicity. The clinical symptoms of the patients and their changes in chest X-ray or CT should be monitored closely. Once a patient shows acute lung symptoms of cough, chest tightness, labored breathing, dyspnea, and hemoptysis of unknown causes, the investigational drug should be interrupted immediately to promptly identify the cause of the symptoms and exclude other causes (such as infection and heart failure). It is recommended to add a chest CT imaging examination, etc. Alveolar lavage fluid analysis and surgical lung biopsy are important means to diagnose interstitial lung disease. Currently, no therapy yields a satisfactory result against pulmonary fibrosis, and correction of hypoxemia and timely administration of corticosteroids are recommended following "Guidelines for Diagnosis and Treatment of Idiopathic Pulmonary (Interstitial) Fibrosis (draft)" issued by the Chinese Medical Association Respiratory Diseases Branch.

Note: The suggestions for the symptomatic treatments of above adverse events are for reference only. For specific countermeasures, please consult a specialist.

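### For acute unexplained lung symptoms, Section 8.3.5 orders an immediate hold without stating a grade, but Section 7.2.1 bars a hold at Grade I and the dose table keeps dosing at Grade I and for up to a week at Grade II

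*Protocol*

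**What the plan says.** Three parts of the protocol bear on the same patient.

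- **Section 8.3.5 (interstitial pulmonary fibrosis).** When a patient develops acute cough, chest tightness, difficulty breathing or hemoptysis without a known cause, "the investigational drug should be interrupted immediately to promptly identify the cause of the symptoms and exclude other causes". No toxicity grade is given.
- **Section 7.2.1 (criteria for interruption or reduction).** "The dose is only allowed to be interrupted and reduced in the case of Grade" III or above for hematological toxicity, or II or above for non-hematological toxicity.
- **Regulations for Dose Modification (the dose table), non-hematological rows.** Grade I keeps the dose as it is. Grade II begins with "Give symptomatic treatment and continue study administration at the same time". Dosing carries on if the event is back to Grade I or lower after a week, and is interrupted if it has not recovered or has worsened. Grades III and IV interrupt.

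Section 8.3 is headed "Recommended Symptomatic Treatment for Common Adverse Drug Reactions" and closes with the note that "The suggestions for the symptomatic treatments of above adverse events are for reference only". Nothing in Section 7, Section 8.3, the dose table or SAP Appendix 1 says which text prevails for lung symptoms.

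**The concern.** A site that reads 7.2.1 and the dose table literally would go on giving study drug while it investigates possible drug-induced lung disease, provided the symptoms are still low grade. An early hold is meant for exactly that situation. The protocol itself states "Currently, no therapy yields a satisfactory result against pulmonary fibrosis", so stopping exposure early is the main protection it offers. It also takes the risk seriously at entry: Section 3.3, item 13, excludes "Patients with previous or current objective evidence of pulmonary fibrosis, interstitial pneumonia, pneumoconiosis, radiation pneumonitis, drug-induced pneumonitis". That criterion governs eligibility only, so it is context and not evidence of a conflict.

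The contradiction also leaves sites exposed on compliance. At Grade I, obeying either text breaks the other. Section 18 tells investigators not to ask the sponsor to approve violations, and to seek a protocol revision if a departure would be better. An amendment is therefore the proper way to resolve this.

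**Working it through.** **Step 1. Compare the instructions by grade, for acute lung symptoms of unknown cause.**

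| Grade | Section 8.3.5 | Section 7.2.1 | Dose table | Result |
|---|---|---|---|---|
| I | Interrupt now | Interruption not permitted | Dose unchanged, no time limit | 8.3.5 contradicts both |
| II | Interrupt now | Interruption permitted | Keep dosing for up to a week unless worse | 8.3.5 contradicts the table only |
| III | Interrupt now | Interruption permitted | Interrupt | All agree |
| IV | Interrupt now | Interruption permitted | Interrupt; stop and withdraw if life-threatening | All agree |

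**Step 2. Is there a rule of precedence?** None is stated. The protocol does have other event-specific drug holds and stops: LVEF (7.2.4), QTcF (7.2.5), liver function (7.2.6 and 7.3), hypertensive crisis (8.3.2), and proteinuria and nephrotic syndrome (8.3.4). They support reading 8.3.5 as another rule of that kind. They do not remove the exclusive wording of 7.2.1.

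**Step 3. Exposure if a site follows the table instead of 8.3.5.** Inputs: once-daily dosing at 750, 500 or 250 mg, a 28-day cycle, and one week in the Grade II row.

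- At 750 mg/day: 7 × 750 = 5,250 mg
- At 500 mg/day: 7 × 500 = 3,500 mg
- At 250 mg/day: 7 × 250 = 1,750 mg
- Share of a cycle: 7/28 = 25%

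These are upper limits per Grade II event, because the week ends early if the toxicity worsens. At Grade I the table sets no limit, so there is no figure to compute.

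**Step 4. The limit on holds.** Section 7.2.2 caps interruption at 2 weeks per cycle: 14/28 = 50%. A hold of 15 days or more in one cycle exceeds it.

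**Step 5. How often might this arise?** The documents do not allow an estimate. Phase I (Section 1.5.1) reports one Grade I case of chest tightness and cough, at 850 mg, which is not shown to have been acute or unexplained. The HCC phase II table of events with incidence of 10% or more (Section 1.5.7) lists no lung symptom.

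**The case against.** The strongest reply is that no sensible investigator would be misled. Section 8.3.5 is a direct instruction about a specific event. It is a diagnostic hold made before the cause is known, whereas 7.2.1 and the table deal with graded toxicity. General grade rules plus event-specific overrides is how the rest of the protocol works. This largely stands, and it is why the point is minor.

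A reader might go further and infer that the lung hold is only advisory, because of its place in Section 8.3 and the closing note. The documents do not support that. Section 8.3 also contains stop rules that are plainly binding: immediate discontinuation and withdrawal for hypertensive crisis, interruption for heavy proteinuria, and withdrawal for nephrotic syndrome. The closing note covers symptomatic treatments, and interrupting study drug is not one.

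A reader might also infer that 7.2.1 lists its exceptions and deliberately leaves lung symptoms out. That does not follow either. The text says fever under 38 °C "with a clear cause can be handled with active symptomatic treatments without the need for dose interruption and dose reduction" and treats controllable nausea and vomiting the same way. Those exceptions waive a hold that the grade would otherwise allow. They are not a list of additional holds.

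What survives is narrow. Section 7.2.1 says interruption is allowed only from Grade II for non-hematological events, and no text exempts 8.3.5. At Grade I the contradiction is literal, and at Grade II the table still points the other way.

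**Conclusion.** The inconsistency is real and limited to low grades: at Grade I between 8.3.5 and both dosing rules, and at Grade II between 8.3.5 and the dose table alone. Its consequence, if a site follows the dosing rules literally, is continued dosing during a work-up for suspected interstitial lung disease. That means up to 7 daily doses per Grade II event and an unspecified number at Grade I. These are amounts of exposure and not estimates of risk, and they arise only if a site sets 8.3.5 aside.

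It would be wrong to infer any effect on the overall survival analysis or a number of patients harmed, since the documents support neither. SAP Appendix 1 has general lines for missed doses (major or critical) and other non-compliance with study drug (minor or major). Neither says which choice at Grade I would be the deviation, but general wording in a deviation table is not itself a fault. This is a low-severity consistency correction, worth making because it concerns patient safety and costs little.

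**What to change.** In Section 7.2.1 and in the Grade I and Grade II non-hematological rows of the dose table, add: *Exception: acute lung symptoms of unknown cause – interrupt immediately regardless of grade, see 8.3.5.*

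Optionally, add to the closing note of Section 8.3 that it does not apply to instructions to interrupt or stop the study drug.

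I would not add a new restart criterion. It is not needed to remove the contradiction. An open-ended hold pending an inconclusive work-up would run into the 2-week limit, and SAP Appendix 1 grades a breach of that limit as critical. Any such rule would also have to respect the Grade IV row, which requires withdrawal for life-threatening reactions.

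The cost is one repeated line, plus the optional sentence, in one amendment. It needs no additional patients or data fields, since the schedule of activities already has a drug interruption form. The downside is a few extra short holds for low-grade symptoms, in both arms because the trial is blinded, and these count toward the 2-week limit per cycle. A site that already follows 8.3.5 faces that limit today.
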